2 OBJECTIVES

Primary objective:

- *Determine whether heparin priming of FNB needle improves tissue quality as compared to standard FNB for EUS-tissue acquisition of pancreatic masses.*

Secondary objectives:

- *Determine whether heparin priming of FNB needle improves cellularity.*
- *Determine whether heparin priming of FNB needle reduces blood contamination.*
- *Determine whether heparin priming of FNB needle improves histologic yield.*
- *Determine whether increasing number of FNB passes affects tissue quality, block contamination, and histologic yield.*
- *Determine the incremental diagnostic yield with a second or third FNB pass as compared to a single FNB pass.*

Hypothesis:

We hypothesize that the tissue quality of EUS-FNB specimens of pancreatic masses decreases with increasing pass number due to blood contamination. This blood contamination can be ameliorated with priming of the needle with an anticoagulant such as heparin, resulting in improved tissue quality of EUS-FNB of pancreatic masses.

Anticipated Results

- *We anticipate that histologic yield will decrease and blood contamination will increase with increasing number of FNB passes*
- *We anticipate that the intervention of heparin priming of the biopsy needle will decrease blood contamination and increase histologic yield.*

Trial design

- Single center, double-blind, superiority, parallel-group, 1:1 ratio, randomized controlled trial

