- Intervention group: The FNB needle will be flushed with 1 mL of heparin (100 USP/mL) and then flushed with air. Pass 1, 2, and 3 will be collected in separate jars and sent to pathology, as per standard clinical procedures. The study will pay for the cost of utilizing and submitting extra jars to pathology so that no extra cost is incurred to the patient for participating in the study. Between passes, after tissue is extracted from the needle, the needle will be flushed with 1 mL of heparin (100 USP/mL) and flushed with air before next pass is made.
- Control group: FNB will be performed as current standard methods in the medical procedure unit without the use of heparin priming. Pass 1, 2, and 3 will be collected in separate jars and sent to pathology, as per standard clinical procedures. The study will pay for the cost of utilizing and submitting extra jars to pathology so that no extra cost is incurred to the patient for participating in the study. Between passes, after tissue is extracted from the needle, the needle will be flushed saline and or air as per current standards of care.

If proceduralist feels that it is unsafe to continue with the research protocol during the procedure (examples would include inadequate tissue acquisition in the clinical jar, or clinical instability of patient during procedure), he or she reserves the right to withdraw the patient from the protocol. For patient safety, the proceduralist will not be blinded to whether the patient was randomized to the heparin or non-heparin arm. If the proceduralist deems more than 3 passes are needed for clinical purposes, the extra passes will go into a fourth jar.

Tissue Analysis:

H&E slides from the passes 1, 2, and 3 (which will be requested from pathology) will be compared in the following manner:

- A blinded clinical pathologist will examine each slide and determine
 - Is a tissue diagnosis able to be made?
 - Is the tissue adequate quality? The pathologist will create a reference scoring system and rate specimens accordingly.
- In parallel, using the HALO® image analysis platform (Indica Labs), each slide will be digitally scanned. The number of cells present on each H&E slide (cell-based analysis), the amount of blood present on each H&E slide (area-based analysis), and the size of each biopsy will be quantified (area-based analysis).

Tracking and labelling system

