7 DATA COLLECTION AND MANAGEMENT PROCEDURES

Collection of medical record data for this study will include the following:

Initial collection:

- Patient demographic data:
 - Age
 - Sex
 - BMI
 - Pack Years
 - Presence of Diabetes, Type 1 or 2
 - Alcohol use
 - History of Pancreatitis
 - History of IPMN (intraductal papillary mucinous neoplasms)
 - Prior Cancer History

Follow up collection (approximately 4 weeks post-procedure):

- Was patient reached for follow-up?
- Did patient develop post-procedural complications?
- Did patient need interventions for post-procedural complications?
- Was hospital admission required for post-procedure complication?
- Did patient require repeated EUS for sampling?
- Age Patient demographic data:

Chart review at end of study (after 98 patients collected)

- Development of new pancreatic disease other than cancer
- Overall survival (date of death)
- Cancer Stage
 - If resectable, did patient receive surgery?
 - If yes
 - What surgery (distal pancreatectomy vs Whipple?)

- Final surgical staging
- Tumor grade
- Chemotherapy treatment
 - Palliative, neoadjuvant, or adjuvant chemo
 - Regimen (FOLFIRINOX, Gemcitabine/abraxane, Gemcitabine/cisplatin)
- ECOG score
- Final Diagnosis

. Data will be pulled from patient's medical charts via both DataDirect and chart review. Regarding data management we will seek assistance with the MICHR database development service. The study team may collect data from each research participant for up to 5 years from when they were consented. This data will be stripped of patient name and stored using REDCap; only the study team members have access to this database. On the database, patient identity will not be discernable to the casual observer. As indicated in section 6, separate from this, a spreadsheet key matching the specimen ID to the patient name and medical record number will be kept in a password and network protected database. Only study team members will have access to this spreadsheet.

SCHEDULE OF EVENTS8 DATA ANALYSIS

Primary Outcomes

- Heparin priming increases cellularity captured in fine needle biopsies
- Heparin priming decrease blood contamination in fine needle biopsies

Secondary Outcomes

- Successive fine needle biopsy passes result in more blood contamination
- Successive fine needle biopsy passes have lower cellular yield
- Successive fine needle biopsy passes have more blood contamination
- Need for repeated procedure (at U of M)

Exploratory Outcomes

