- Identify correlations in patient metadata (i.e. tumor grade, cancer stage) and tissue quality, cellular yield, and blood contamination

Tissue analysis:

H&E slides from the pass 1, 2, and 3 (which will be requested from pathology) will be compared in the following manner:

- A blinded clinical pathologist will examine each slide and determine
 - Is a tissue diagnosis able to be made?
 - Is the tissue adequate quality (pathologist will make a reference scoring system and rank specimens accordingly)

In parallel, using image processing software, the number of cells present on each H&E slide will be quantified, the amount of blood present on each H&E slide will be quantified by area quantification, and the tissue yield on each H&E slide will be quantified by area quantification.

Statistical Comparisons using image analysis:

The student *t* test will be utilized to assess if there is a significant difference in the following:

- Blood contamination area between passes 1, 2, and 3 in the heparin group
- Blood contamination area between passes 1, 2, and 3 in the non-heparin group
- Blood contamination area in pass 1 between the heparin group and non-heparin group
- Blood contamination area in pass 2 between the heparin group and non-heparin group
- Blood contamination area in pass 3 between the heparin group and non-heparin group
- Tissue area between passes 1, 2, and 3 in the heparin group
- Tissue area between passes 1, 2, and 3 in the non-heparin group
- Tissue area in pass 1 between the heparin group and non-heparin group
- Tissue area in pass 2 between the heparin group and non-heparin group
- Tissue area in pass 3 between the heparin group and non-heparin group
- Cell number between passes 1, 2, and 3 in the heparin group
- Cell number between passes 1, 2, and 3 in the non-heparin group
- Cell number in pass 1 between the heparin group and non-heparin group
- Cell number in pass 2 between the heparin group and non-heparin group
- Cell number in pass 3 between the heparin group and non-heparin group

Statistical Comparisons using pathologist scoring:

The Pearson's Chi-squared test will be utilized to determine if there is a significant difference in the following:

- Tissue score between passes 1, 2, and 3 in the heparin group
- Tissue score between passes 1, 2, and 3 in the non-heparin group
- Tissue score in pass 1 between the heparin and non-heparin group
- Tissue score in pass 2 between the heparin and non-heparin group

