- Tissue score in pass 3 between the heparin and non-heparin group

In a previous study the standard deviation for tissue area with fine needle biopsy of pancreatic masses was 5 mm².⁹ Based on our preliminary results and on results of

recent crossover RCT, we will assume a difference between randomized groups of 3 mm².⁵ Therefore, if the true mean difference in total tissue area between the heparin and non-heparin groups is 3 mm², we will need to study 44 subjects in the heparin group and 44 subjects in the non-heparin group, to reject the null hypothesis with 80% power and with a type I error of 0.05. To account for 10% dropouts, we will need to recruit 98 subjects.

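### If the pathologist's tissue score has three or more ordered grades, Pearson's chi-squared ignores their order and costs power in the between-arm comparisons; the number of levels is not stated

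*Combined protocol and SAP*

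**What the plan says.** Section 8, under the comparisons that use pathologist scoring, states that Pearson's "Chi-squared test will be utilized to determine if there is a significant difference in the following". Five comparisons follow. Three are between arms, one at each pass (for example "Tissue score in pass 1 between the heparin and non-heparin group"). Two are between passes 1, 2 and 3 within an arm. No rank, trend or ordinal method is named for the score.

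The scale itself is still to be built. Section 6 says "The pathologist will create a reference scoring system and rate specimens accordingly". Section 8 puts it as "Is the tissue adequate quality (pathologist will make a reference scoring system and rank specimens accordingly". Neither section gives the number of levels, their definitions or a cut-off for adequacy.

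On the standing of the score, the primary objective in Section 2 is to "Determine whether heparin priming of FNB needle improves tissue quality as compared to standard FNB". The primary outcomes in Section 8 are cellularity ("Heparin priming increases cellularity captured in fine needle biopsies") and blood contamination. The pathologist's score is not among the primary or secondary outcomes there; tissue quality appears in the outcome lists only within an exploratory correlation. The one power calculation with inputs is for tissue area and arrives at "44 subjects in the heparin group and 44 subjects in the non-heparin group".

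**The concern.** A quality rating with more than two levels is ordered, and the hypothesis in Section 2 has a direction: heparin is expected to improve quality. Pearson's chi-squared treats the grades as unordered labels. With k grades it spreads the test over k − 1 degrees of freedom, most of them spent on patterns that the trial does not hypothesise. A rank or trend test puts its single degree of freedom on the shift of interest.

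What is at stake is the chance of detecting a real improvement on the measure that speaks most directly to the primary objective, in a trial with about 44 evaluable patients per arm. The plan also names no effect estimate for the score, so a significant chi-squared result would say that the distributions differ without summarising by how much or in which direction.

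**Working it through.** **1. The plan's own figure.** Inputs from Section 8: difference 3 mm², SD 5 mm², alpha 0.05 (two-sided assumed), power 80%, dropout 10%.

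n per arm = 2 × (1.960 + 0.842)² × 5² / 3² = 2 × 7.85 × 25 / 9 = 43.6, so 44. Recruited: 88 / 0.90 = 97.8, so 98. Both figures reproduce. They concern tissue area; no such calculation exists for the score.

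**2. Cost of the extra degrees of freedom.** Take an effect for which a one-degree-of-freedom ordered test has 80% power, that is, noncentrality 7.85. If Pearson's test has the same noncentrality on k − 1 degrees of freedom, its power is P(χ²(k − 1; 7.85) > 5% critical value):

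| Grades | df | Critical value | Power of Pearson | Loss from 80% |
|---|---|---|---|---|
| 2 | 1 | 3.84 | 80% | 0 |
| 3 | 2 | 5.99 | 71% | 9 points |
| 4 | 3 | 7.81 | 64.5% | about 16 points |
| 5 | 4 | 9.49 | 60% | about 20 points |
| 6 | 5 | 11.07 | 56% | about 24 points |

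**3. Simulation at the trial's size.** 44 per arm, 20,000 trials per scenario, Pearson's chi-squared against the tie-corrected Wilcoxon test. The number of grades, the grade distribution in the control arm and the size of the shift are all assumptions, because the documents give none of them.

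| Grades | Odds ratio 3: Pearson vs Wilcoxon | Odds ratio 2.5: Pearson vs Wilcoxon | Loss over odds ratios 2 to 4 and several control distributions |
|---|---|---|---|
| 3 | 68% vs 78% | 52% vs 63% | 5 to 11 points |
| 4 | 64% vs 80% | 47% vs 65% | 8 to 18 points |
| 5 | 60% vs 81% | 44% vs 67% | 13 to 24 points |

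With two grades the tests agree apart from a trivial factor: the squared Wilcoxon statistic is (N − 1)/N = 87/88 of Pearson's. In one two-grade case at odds ratio 3, power was 63% and 62%. With six grades the loss reached about 28 points. Under no effect, both tests rejected in about 5% of trials.

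**4. A shift tied to the plan's own effect size.** The tissue-area assumption is a standardised difference of 3/5 = 0.6. If quality had a latent normal shift of 0.6 SD, cut into equally frequent grades, Pearson against Wilcoxon gives 59% vs 69% (3 grades), 56% vs 73% (4) and 52% vs 75% (5).

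**5. If nobody drops out.** At 98/2 = 49 per arm, five equally frequent grades and odds ratio 3 give 65% vs 85%. The gap is much the same.

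**6. Where Pearson does better.** In one example with a non-monotone difference between arms, Pearson had 71% power and the Wilcoxon test 6%.

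**The case against.** The strongest reply is that the score may be binary. Both sections pose the matter as whether the tissue is of adequate quality. A yes/no answer is a natural reading, it fits the choice of chi-squared, and it would lose nothing. This stands, and it makes the point conditional. It does not remove it: a scoring system by which specimens are rated suggests that more than two levels are at least possible, and naming an ordered test now costs nothing if there turn out to be two.

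It is also fair to say that a two-sided Wilcoxon p-value shows direction no better than Pearson's does. Direction and size come from an estimate by arm, which is why the fix asks for one.

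A reader might infer from "pathologist will make a reference scoring system and rank specimens accordingly" that specimens will be put in literal rank order and chi-squared run on the ranks. The documents do not support that. The ranking follows a scoring system, and Section 6 uses rate for the same step. This is loose wording that should be aligned.

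Finally, the two comparisons between passes within an arm have a larger fault than grade order. Three specimens from one patient are not independent, and both Pearson's test and an ordinary rank-sum test assume that they are.

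**Conclusion.** The point holds as a conditional loss of efficiency. It is zero with a binary score. At 44 per arm it is about 5 to 11 points of power with 3 grades, 8 to 18 with 4 and 13 to 24 with 5. These ranges rest on an assumed proportional odds ratio of 2 to 4, assumed grade distributions and a shift in one direction. No single figure can be called the trial's loss, or its upper limit, until the scale exists.

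Two stronger conclusions are tempting. One is that the between-arm chi-squared tests are invalid; they are not, since their type I error is about 5%. The other is that the trial forfeits part of its planned 80% power. It does not: that figure belongs to tissue area, and the score is neither a listed primary or secondary outcome nor given a power target. The mismatch between the primary objective and the listed primary outcomes is a separate matter and does not enlarge this one.

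**What to change.** - Define the scoring scale, its levels and any adequacy cut-off in the protocol before slides are read, and use rate in both Section 6 and Section 8.
- For the between-arm score comparisons at passes 1, 2 and 3, replace Pearson's chi-squared with a tie-corrected Wilcoxon rank-sum test or a linear trend test. Report a proportional odds ratio with a 95% CI. Keep chi-squared only if the score is binary.
- For the comparisons between passes within an arm, name a method for paired or repeated ordinal data, such as an ordinal mixed or GEE model with patient as the cluster. The between-arm change does not cover these.

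The cost is a few sentences, with no extra data or patients. The downside is less sensitivity to a non-monotone difference between arms, which is not the trial's hypothesis. Fixing the scale and the test before any scores exist also avoids a choice of test made with the scores in view.

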6 STUDY DESIGN AND PROCEDURES

Study setting: University of Michigan- Medical Procedure Unit

Study type: Clinical Trial

Assignment of Interventions:

Enrollment: 98 patients

Randomization: Subjects will be randomized in a 1:1 allocation ratio to the heparin group or the non-heparin control group at the time of intra-procedural decision to sample the mass. We will use restrictive block randomization to ensure balanced number of participants per group. The randomization sequence will be generated centrally from a computerized binary number generator at the University of Michigan. The treatment assignments will be in opaque sealed envelopes for allocation concealment. The study coordinator will enroll participants and will assign participants to the intervention. The randomization key will be kept under lock by the study coordinator until completion of the study period.

Blinding: The participants and the pathologist will be blinded to the group allocation. The proceduralist will not be blinded to allocation given the design of the study and for patient safety.

Interventions: all subjects will undergo EUS-FNB using linear echoendoscopes (GF-UCT180 Olympus America, Center Valley, Pa, USA). All EUS-FNB procedures will be performed by 1 of 5 experienced endosonographers ([name]). Once the site is identified, the lesion will be punctured using a 22-gauge Fork-tip needle (Sharkcore needle). The sampling technique will be at the discretion of the endoscopist (e.g. stylet vs. not stylet, suction vs. not suction, fanning technique vs. to-and-fro technique, number of strokes). A total of 3 FNB passes will be performed on every procedure. The use of rapid on-site cytopathology (ROSE) will be used at the discretion of the endoscopist and will not be mandatory for this study. The tissue specimens from each the 3 passes will be collected in 3 separate jars of 10% formalin for tissue analysis. The use of heparin flushing vs. not heparin flushing, will be based on their randomized group assignments:

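### Within-arm tests of tissue score across passes 1, 2 and 3 use Pearson's chi-squared on repeated measures from the same patients; the matching t-test lines do not say how three passes are compared

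*Combined protocol and SAP*

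**What the plan says.** - Section 6, Interventions: "A total of 3 FNB passes will be performed on every procedure". Each pass goes into its own jar and is examined separately.
- Section 8, comparisons by pathologist scoring: Pearson's "Chi-squared test will be utilized to determine if there is a significant difference in the following". The list includes "Tissue score between passes 1, 2, and 3 in the heparin group" and the same line for the non-heparin group. The remaining score lines compare the arms at a single pass.
- Section 8, comparisons by image analysis: the Student t "test will be utilized to assess if there is a significant difference in the following". The list includes "Blood contamination area between passes 1, 2, and 3 in the heparin group". The same line appears for the non-heparin group, and for tissue area and cell number in both groups, which makes six lines.
- Section 8, Tissue analysis, leaves the score scale open: "pathologist will make a reference scoring system and rank specimens accordingly". Section 6 speaks of rating rather than ranking, under a yes/no question about adequacy.
- The pass effect is a secondary objective in section 2: "Determine whether increasing number of FNB passes affects tissue quality, block contamination, and histologic yield". It is also among the section 8 secondary outcomes: "Successive fine needle biopsy passes result in more blood contamination".
- Section 10 refers back to section 8 for the tests. No section mentions pairing, repeated measures, named pass contrasts or adjustment for several contrasts.

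**The concern.** A table of pass by score counts each patient three times, whereas Pearson's chi-squared treats the entries as separate patients. A lesion that gives good tissue on one pass probably tends to do so on the next. The between-patient variation then cancels from the comparison of passes, but the test still charges for it. The true error rate falls below 5% and power falls with it.

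The likely mistake is to miss a real fall in quality over successive passes. Section 1 says the results will guide how many passes to take and how to divide them between uses, so a missed decline would mislead that guidance.

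The t-test lines raise a different problem. A t test compares two means, and three passes are listed. An unpaired reading is conservative under positive correlation. A paired reading with three unadjusted contrasts gives too many false positives. The plan does not say which applies.

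**Working it through.** **The plan's own figure.** Section 8 gives a difference of 3 mm², SD 5 mm², 80% power and type I error 0.05 (taken as two-sided). Then n = 2(1.96 + 0.84)² × 5² / 3² = 43.6, so 44 per arm, and 88/0.9 = 97.8, so 98 recruited. Both figures reproduce. They concern a comparison between arms and are not touched by this point.

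**Inputs for the check.** 44 patients in an arm (section 8), three passes each (section 6), two-sided 0.05. Assumptions not in the documents: correlation between passes, size of the decline, a two-level score, equal SD at each pass.

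**Score lines, error rate.** Let r be the correlation between passes on the observed binary score, equal for all pairs. With no pass effect, Pearson's statistic on the 3 × 2 table behaves approximately as (1 − r) times a chi-squared variable with 2 df. Its actual error rate is therefore about 0.05^(1/(1−r)):

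- r = 0.18: 0.05^1.22 = 2.6%
- r = 0.32: 0.05^1.47 = 1.2%
- r = 0.48: 0.05^1.92 = 0.3%

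At 70% adequate, these three values of r correspond to correlations of 0.3, 0.5 and 0.7 on an underlying normal scale. The scale matters: if 0.5 were the correlation of the observed score itself, the error rate would be 0.05² = 0.25%.

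**Score lines, simulation.** A latent-normal binary score agrees with the formula to within rounding and simulation error. Power is for adequacy of 85/75/65% at passes 1/2/3.

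| Latent correlation (observed, at 70% adequate) | Chi-squared type I error | Cochran's Q type I error | Power, chi-squared | Power, Cochran's Q |
|---|---|---|---|---|
| 0 (0) | 5% | about 5% | 49% | 48% |
| 0.3 (0.18) | 3% | about 5% | 46% | 56% |
| 0.5 (0.32) | 1.4% | about 5% | 45% | 63% |
| 0.7 (0.48) | 0.4% | about 5% | 42% | 75% |

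**Image lines.** Take a linear fall of 0.4 SD from pass 1 to pass 3, with correlation ρ between passes. The SD of a within-patient difference is √(2(1−ρ)) in units of the per-pass SD. The expected paired t statistic is about 0.4√44/√(2(1−ρ)), which is 1.88 / 2.24 / 2.65 / 3.42 at ρ = 0 / 0.3 / 0.5 / 0.7. An unpaired test ignores ρ in its standard error and stays near 1.88.

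| ρ | Power, unpaired t | Power, paired t, unadjusted | Power, joint test first, then paired t |
|---|---|---|---|
| 0 | about 45% | 45% | 32% |
| 0.3 | about 45% | 59% | 45% |
| 0.5 | about 44% | 73% | 61% |
| 0.7 | about 43% | 92% | 84% |

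With no pass effect, three unadjusted paired tests give at least one false positive about 12% of the time at every ρ. (Three independent tests would give 1 − 0.95³ = 14.3%; these share passes.) Three unadjusted unpaired tests give 12 / 5 / 1.8 / 0.2%. Requiring a significant joint test first holds the familywise rate near 5%. With only three passes no further adjustment is needed, because once one pair truly differs, at most one true null pairwise hypothesis remains.

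**The case against.** The strongest reply is that little is at risk. Section 1 calls the trial a pilot, and the affected lines serve secondary questions. The chi-squared error is conservative, so it creates no false claim. The documents give no correlation between passes, and at zero correlation a binary score loses nothing. All of this stands. It limits the weight of the point, but it does not make the test right for the two score lines.

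A reader might infer more than the text supports:

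- *That the six t tests are wrong.* A Student t test may be paired, and section 8 does not exclude it. What is missing is the pairing, the contrasts and the error control.
- *That the chi-squared test produces false positives.* With positive correlation it does the opposite. Inflation arises only if paired contrasts are run without adjustment.
- *That chi-squared is also faulty for ignoring the order of the score.* The scale has not been defined: section 6 says rate, section 8 says rank. If the score is binary there is no order to lose. The same complaint would also reach the per-pass comparisons between arms, where chi-squared is a valid test.
- *That the plan must test whether the change over passes differs by arm.* Section 1 asks whether heparin mitigates a decline, but no objective or outcome requires that contrast, and the per-pass comparisons bear on it indirectly.
- *That the primary analysis or the sample size is compromised.* Per-pass comparisons between arms involve different patients and do not depend on how passes correlate.

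**Conclusion.** The point holds for two lines as an error and for six as a gap. Pearson's chi-squared is the wrong test for tissue score across passes within an arm, because the same patients supply all three passes.

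The size depends on assumptions. For a binary score with 44 patients per arm, the loss of power against Cochran's Q runs from nothing at zero correlation, through 46 v 56% and 45 v 63%, to 42 v 75% at latent correlations of 0.3, 0.5 and 0.7. A three-level or longer scale would give different figures. The image-analysis lines cannot be judged right or wrong until the plan says how three passes enter a two-mean test.

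This should be settled before analysis, so that the choice between paired and unpaired tests is not made with the results in view.

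**What to change.** Suggested wording for section 8:

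> Tissue score across passes 1, 2 and 3 within each arm will be compared with Cochran's Q if the score is binary, or the Friedman test if it is ordinal, or with a logistic or ordinal model clustered on patient. Blood area, tissue area and cell number across passes within each arm will be compared with a joint within-patient test of pass (mixed model or repeated-measures test). Paired contrasts between passes will be tested only if the joint test is significant at 0.05.

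Define the score scale at the same time, since the choice of test depends on it. Cochran's Q and Friedman need all three passes, and section 6 allows withdrawal during the procedure. A model can use the passes available, provided those slides are kept, which the documents do not say. Inadequate tissue is one stated reason for withdrawal, so missing passes may not be random.

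Optional: report the between-arm difference in the pass 1 to pass 3 change with its 95% confidence interval, as a supportive estimate.

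Cost: wording and a little analysis time, with no new patients, data or procedures. The joint test costs power for pass 1 v 3 against an unadjusted paired test (32 / 45 / 61 / 84% against 45 / 59 / 73 / 92% in the example). At zero correlation it is also below an unadjusted unpaired test (32% against about 45%). The per-pass comparisons between arms need no change on this account.

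### Sections 2 and 8 name different primary outcomes, and the 80% power claim is calculated for total tissue area, which is primary in neither

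*Combined protocol and SAP*

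**What the plan says.** - **Section 2, primary objective:** "Determine whether heparin priming of FNB needle improves tissue quality as compared to standard FNB".
- **Section 2, secondary objectives:** these include "Determine whether heparin priming of FNB needle improves cellularity" and "Determine whether heparin priming of FNB needle reduces blood contamination". Histologic yield is also listed as secondary.
- **Section 8, Primary Outcomes:** "Heparin priming increases cellularity captured in fine needle biopsies" and "Heparin priming decrease blood contamination in fine needle biopsies". Tissue quality is neither a primary nor a secondary outcome there; it appears among the exploratory correlations.
- **How each variable is measured (Sections 6 and 8):** tissue quality is judged by a blinded pathologist: "The pathologist will create a reference scoring system and rate specimens accordingly". Image analysis runs in parallel and gives cell number, blood area and tissue area; for the last, "the tissue yield on each H&E slide will be quantified by area quantification". The score is compared by chi-squared test and the image measures by t test, with between-arm comparisons at passes 1, 2 and 3 separately.
- **Section 8, sample size:** the calculation takes an SD of 5 mm² for tissue area and a difference of 3 mm², and asks what is needed "if the true mean difference in total tissue area between the heparin and non-heparin groups" has that value. It arrives at 44 per arm for 80% power at a type I error of 0.05, and 98 recruited to allow for 10% dropout.
- **Section 10:** power of 0.80 is claimed for comparisons on both pass number and heparin priming. No outcome, effect or SD is given, and the size is stated as 50 per arm and 98 in total.

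**The concern.** The same two variables are secondary in one section and primary in another, and the trial is sized on a third variable. Two things follow.

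First, the power statement does not describe the trial's ability to answer its own primary question, whichever section is followed.

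Second, nothing fixes which result decides the trial. The Section 8 primaries correspond to six between-arm t tests (two variables at three passes), and the Section 2 primary to three chi-squared tests. That makes nine candidates, with no deciding test and no multiplicity rule, so the result reported as primary could be chosen after the data are seen. As an illustration, six independent tests at 0.05 would give a chance of 1 − 0.95⁶ = 26% of at least one false positive. The passes are correlated, so the true figure would differ.

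A smaller question sits inside the calculation. The SD is given for tissue area and the difference for total tissue area, while tissue is measured slide by slide. The plan does not say whether either figure is per pass or summed over three passes.

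**Working it through.** **1. Reproduce the plan's figure.** Inputs from Section 8: difference 3 mm², SD 5 mm², power 80%, alpha 0.05 (taken as two-sided; one-sided would give 35 per arm, which does not match).

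- n per arm = 2(1.960 + 0.842)² / (3/5)² = 43.6, so 44.
- Noncentral-t power at 44 per arm for 0.6 SD = 79.5%.
- Dropout: 88/0.9 = 97.8, so 98, which is 49 per arm at 1:1.

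The calculation is sound for the variable it uses. In Section 10, 50 per arm would be 100, not 98.

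**2. Match the powered variable to the named primaries.**

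| Variable | Section 2 | Section 8 | Power inputs given |
|---|---|---|---|
| Tissue quality (pathologist score) | Primary | Exploratory only | None |
| Cellularity (cell number) | Secondary | Primary | None |
| Blood contamination (blood area) | Secondary | Primary | None |
| Tissue area | At most secondary, if read as histologic yield | Not a named outcome | 3 mm², SD 5 mm² |

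Only the last row has inputs, and it is the only row that is primary nowhere.

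**3. What 44 per arm gives the Section 8 primaries.** With no inputs in the plan, the standardised difference has to be assumed. Noncentral-t power for one two-sided test:

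| True difference (SD units, assumed) | Power at alpha 0.05 | Power at alpha 0.025 |
|---|---|---|
| 0.3 | 29% | 20% |
| 0.4 | 46% | 35% |
| 0.5 | 64% | 53% |
| 0.6 | 79% | 70% |

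The difference detectable with 80% power is (z + 0.842)√(2/44) = 0.597 SD at 0.05 and 0.657 SD at 0.025. For the t test it is 0.604 and 0.667.

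**4. What 44 per arm gives the Section 2 primary.** If the score were reduced to adequate or inadequate (an assumption, since the scoring system is not yet defined), 80% power by the pooled-variance formula needs about 50% vs 78%, or 70% vs 93%. The control rates are assumed.

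**5. Does the claim hold for the listed tissue-area tests?** That depends on the unstated unit. Let ρ be the between-pass correlation (assumed) and let all passes have equal variance. The SD of a three-pass sum is then the per-pass SD times √(3 + 6ρ).

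- *Both figures per pass.* Each per-pass test has 79.5% power. With the same effect at each pass, the three-pass sum has difference 9 and SD 5√(3 + 6ρ), so power runs from 99.8% (ρ = 0) to 79.5% (ρ = 1).
- *Both figures three-pass totals.* No listed test matches the calculation. With an equal effect of 3/3 = 1 mm² per pass and per-pass SD 5/√(3 + 6ρ), each per-pass test has 36%, 53%, 62% or 70% power at ρ = 0, 0.3, 0.5 or 0.7. If the effect instead grows as 0.5, 1.0 and 1.5 mm² over the passes (assumed, ρ = 0.5), power is 21%, 62% and 93%.
- *SD per pass, difference a total.* The SD of the total is 8.66 (ρ = 0) to 15 (ρ = 1), and power for the total falls from 36% to 15%.

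**The case against.** The strongest reply is that tissue quality is an umbrella term. The Section 2 hypothesis links less blood contamination to better tissue quality, so cellularity, blood and area could all be seen as measures of it, and the two sections would then agree. The text does not support this far enough. Section 2 lists cellularity and blood contamination as separate secondary objectives, and Sections 6 and 8 give quality its own pathologist score, beside the image measures and with a different test. Even on the umbrella reading, area is not a named primary. Reading histologic yield as tissue area is reasonable, but Section 2 makes that a secondary objective.

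A second reply is that Section 1 calls the trial a pilot, that every variable is measured on every slide, and that no data are lost. This does limit the harm. It does not withdraw the 80% claims in Sections 8 and 10, and Section 2 describes a superiority trial. The unfixed primary is the weightier half of the point; the power mismatch alone would matter less.

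It is also fair to say that the unit scenarios in step 5 rest on assumed correlations and effect patterns, and that the cited sources might settle the unit. They show why the unit must be stated. The main finding does not depend on them, nor on the Section 10 slip.

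**Conclusion.** The concern holds. The current text names conflicting primaries, and the only supported power figure is for a variable that is primary in neither section and whose total has no listed between-arm test. The mismatch itself needs no assumption.

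Its effect on power cannot be reduced to one number, because the plan gives no effect or SD for any named primary. What can be said is that 44 per arm gives 80% power only for a true difference of about 0.60 SD in a single t test at 0.05, and nothing in the plan shows that cell number or blood area will differ by that much. This should be corrected before outcome data are seen.

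**What to change.** 1. **One primary, one test.** Name the same primary outcome in Sections 2 and 8. In Section 8, list a single deciding between-arm test for it at two-sided 0.05, either at a stated pass or on a stated per-patient summary of passes 1 to 3. The choice of outcome is the sponsor's and should be fixed before outcome data are seen.
2. **Unit.** State in Section 8 whether 3 mm² and 5 mm² are per pass or three-pass totals.
3. **Power claim.** Keep 80% only if tissue area, in the unit both figures describe, is the primary.
   - If cellularity or blood contamination stays primary, replace the claim with the detectable difference at 44 per arm, about 0.60 SD at 0.05. If both stay primary and either suffices, it is about 0.67 SD at 0.025 each, with one test per outcome.
   - If tissue quality is primary, drop the claim and state the detectable difference in the score once its levels are defined; step 4 shows the order of size for a two-level score.
4. **Section 10.** State 49 randomised per arm (44 evaluable), 98 in total, and limit the power claim to the one deciding comparison.

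The cost is wording in Sections 2, 8 and 10 and one named test, with no new measurement and no more patients. The sample stays at 98 because an unsupported 80% is replaced by a detectable difference; a sponsor who wants 80% power for a smaller effect on another primary would need more patients. The power claim becomes narrower, and would have to be withdrawn if 3 mm² and 5 mm² prove to be in different units.
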